#### Rationale

Lung-protective intraoperative ventilation (LPV) has the potential to improve the outcome of surgery patients through a reduction in postoperative pulmonary complications [1, 2]. Use of intraoperative ventilation strategies that use a low tidal volume could result in intraoperative hypercapnia. However, hypocapnia remains surprisingly common during intraoperative ventilation [3, 4], possibly meaning that anesthesiologists continue to use high, if not too high respiratory rates or tidal volumes.

Previous studies suggested associations between intraoperative derangement of end-tidal carbon dioxide (etCO2) and postoperative outcomes [5, 6]. Indeed, two studies in highly selected patient groups showed associations of intraoperative hypocapnia with prolonged length of hospital stay, in patients undergoing pancreaticoduodonectomy [7], and in patients undergoing hysterectomy [8].

To gain a better understanding of the epidemiology of intraoperative hypocapnia, in particular the associations of intraoperative hypocapnia with patient demographics, ventilator characteristics, and perioperative complications we will perform an Individual patient–level meta–analysis of two recent randomized clinical trials of intraoperative ventilation [3, 9].

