#### Hypothesis

Intraoperative hypocapnia has an independent association with patient demographics, ventilation parameters, and perioperative complications.

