# Objectives

The current analysis will assess associations of intraoperative hypocapnia with patient demographics, ventilation characteristics, occurrence of intraoperative complications, postoperative pulmonary complications, and length of hospital stay in patients undergoing planned major surgery [3, 9].

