#### Study outcomes

The primary outcome of this analysis is a composite of predefined and collected postoperative pulmonary complications within the first seven days after the surgery, as used in the parent studies. Postoperative pulmonary complications included mild, moderate, and severe respiratory failure; acute respiratory distress syndrome; bronchospasm; new pulmonary infiltrate; pulmonary infection; aspiration pneumonitis; pleural effusions; atelectasis; cardiopulmonary edema; and pneumothorax.

Secondary outcomes include intraoperative complications, a set of intraoperative ventilation parameters, intraoperative vital signs (heart rate, mean

3

arterial pressure, and SpO2) and any new arrhythmias needing intervention. Other endpoints are unexpected need for intensive care unit admission, ICU readmission, and length of stay in hospital up till day 90.

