# Statistical analysis plan

Demographic, clinical and outcome variables are presented as medians with interquartile ranges (IQR), or number with percentage, where appropriate. Differences in baseline characteristics between patients with and patients without hypocapnia will be analyzed using the Pearson Chi–squared or Fisher exact tests for categorical variables and with a one–way ANOVA or Kruskal–Wallis test for continuous variables.

Data points for intraoperative variables (vital signs, ventilator settings and ventilation parameters) will include those collected in the first, second and third hour after start of the study, and before extubation.

Occurrence of postoperative pulmonary complications will be compared using a Fisher's exact test, time to event analyses will be performed using a Cox proportional hazard model or a competing risk model where appropriate. Next, we will perform a propensity matched cohort. Patients will be matched 1:1 with a maximum caliper of 0.02. The following covariates will be used for propensity matching: age, gender, BMI, type of surgery, compliance, history of COPD. We will calculate interaction term for the ARISCAT score as sensitivity analysis. We will perform time-weighted analysis for etCO2 levels in the primary end-points. Kaplan-Meier curve will be used to plot the relation between hypocapnia and the primary outcome.

A LOESS regression will be used to visualize the relationship of etCO2 as a continuous variable with the primary outcome. The association between etCO2 and the primary outcome will be determined using a generalized mixed model in which age, gender, BMI, type of surgery, compliance and history of COPD will be used as covariates. Sankey plot will be used to demonstrate flow association between etCO2 and primary or secondary outcomes.

As a sensitivity analysis the main analyses will be repeated in obese patients and non-obese patients, using a cutoff of 30 kg/m^2 for BMI. Another sensitivity analysis will be performed to determine the effect of PEEP settings on outcome. For this analysis the interaction term for PEEP on the generalized mixed model will be calculated.

A P–value of < 0.05 will be considered statistically significant. All analyses will be performed with R statistics version 4.0.4.

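### The plan hypothesises an 'independent' association of hypocapnia with complications, but no planned analysis adjusts for tidal volume or respiratory rate

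*Combined protocol and SAP*

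**What the plan says.** All references are to the combined protocol and SAP.

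- **Rationale.** Hypocapnia remains common, "possibly meaning that anesthesiologists continue to use high, if not too high respiratory rates or tidal volumes". The same section says that lung-protective ventilation "has the potential to improve the outcome of surgery patients through a reduction in postoperative pulmonary complications".
- **Hypothesis.** "Intraoperative hypocapnia has an independent association with patient demographics, ventilation parameters, and perioperative complications".
- **Study outcomes.** A PPC composite is primary. Ventilation parameters also appear as outcomes: "Secondary outcomes include intraoperative complications, a set of intraoperative ventilation parameters".
- **Calculations.** VT and RR are among the variables collected in the parent trials.
- **Statistical analysis plan, match.** "The following covariates will be used for propensity matching: age, gender, BMI, type of surgery, compliance, history of COPD".
- **Statistical analysis plan, model.** The association of etCO2 with the primary outcome comes from a "generalized mixed model in which age, gender, BMI, type of surgery, compliance and history of COPD will be used as covariates".
- **Statistical analysis plan, ventilator settings.** The only setting that enters an outcome analysis is PEEP, in a sensitivity analysis where "the interaction term for PEEP on the generalized mixed model will be calculated".

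**The concern.** The plan itself suggests both arms of a confounding path. High VT or RR may produce hypocapnia, and the way a patient is ventilated may change the risk of PPCs. If VT or RR affects PPCs by a route other than etCO2, part of any hypocapnia–PPC association reflects ventilation. Neither adjusted analysis would show how much.

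What is at stake is the interpretation of the main result. A reader who sees an 'independent' association will ask whether low etCO2 is more than a marker of higher VT or RR. The data to examine this are held, but no adjusted analysis is scheduled to do so.

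**Working it through.** The plan states no effect size, event count or target sample size, so there is no figure to reproduce. The check has two parts: an audit of the analyses, and an illustration in which every input is assumed.

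**1. Where VT and RR enter the analysis of PPCs**

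| Analysis in the Statistical analysis plan | VT or RR included? |
|---|---|
| Propensity match (six covariates) | No |
| Generalized mixed model (same six) | No |
| Cox or competing-risk model | No covariates named |
| ARISCAT interaction | No |
| Time-weighted etCO2 | No; changes the exposure measure only |
| Split at BMI 30 kg/m² | No |
| PEEP interaction | No |

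Two items come close without filling the gap. Compliance is VT divided by driving pressure (Calculations), so it carries some information on VT, but it does not hold VT fixed and contains no RR. The PEEP interaction examines effect modification by PEEP. Table 2, eTable 2 and Figure 3 (Planned inserts) can show a ventilation imbalance but do not take it out of an estimate.

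**2. How large a spurious association could be**

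Assumptions: hypocapnia has no effect on PPCs; 60% of patients are hypocapnic; PPC risk is 30%; etCO2 and a ventilation intensity V are bivariate normal with correlation ρ; V has a PPC odds ratio (OR) of 1.2 or 1.3 per SD; no other covariates.

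With 60% below the cutoff, z = 0.253 and the normal density there is φ(z) = 0.386. The two groups differ in mean etCO2 by 0.386/0.6 + 0.386/0.4 = 1.61 SD, and so in mean V by 1.61 × |ρ| SD. Approximately,

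spurious log OR = 1.61 × |ρ| × ln(OR per SD of V).

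| ρ | V effect 1.2 per SD | V effect 1.3 per SD |
|---|---|---|
| -0.2 | exp(0.322 × 0.182) = 1.06 | exp(0.322 × 0.262) = 1.09 |
| -0.3 | exp(0.483 × 0.182) = 1.09 | exp(0.483 × 0.262) = 1.13 |
| -0.5 | exp(0.805 × 0.182) = 1.16 | exp(0.805 × 0.262) = 1.23 |

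Exact logistic fits by numerical integration give the same values to two decimals. If V has no PPC effect of its own, the result is 1.00. If only VT matters and its range is narrow (ρ of -0.1 to -0.2), the formula gives 1.03 to 1.09.

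A separate simulation made etCO2 depend directly on VT × RR and kept compliance in the model, with 40% hypocapnic. With no VT or RR effect on PPCs the OR was 1.00. It was 1.14 with a VT effect of 1.2 per ml/kg, 1.10 with an RR effect of 1.05 per breath/min, 1.27 with both, and 1.64 with 1.5 and 1.1. Adding VT and RR returned 0.99 to 1.01, but that assumes perfectly measured values that do not respond to etCO2.

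**3. What one early value of VT and RR would remove**

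In the setting of step 2, an early value correlated 0.8 with the relevant intensity removes 60–63% of the spurious log OR; one correlated 0.6 removes 32–35%. The OR of 1.23 falls to 1.09 or 1.15.

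**4. Cost in precision**

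The standard error grows by about 1/√(1 − R²), where R is the correlation of hypocapnia with the added variable. At ρ = -0.5 and a perfect measure, R = 0.5 × 0.386/√(0.6 × 0.4) = 0.394, so R² = 0.155 and the factor is 1.09. Across ρ of -0.2 to -0.5 the increase is about 1–9%. In the simulation where etCO2 tracks VT × RR closely it was about 1.3 times, which corresponds to R² = 1 − 1/1.3² = 0.41.

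**The case against.** **'Independent' may not mean independent of ventilation.** The Hypothesis does not say independent of what, and the same sentence names ventilation parameters as something hypocapnia is associated with. The Objectives are plainer still: "The current analysis will assess associations of intraoperative hypocapnia with patient demographics, ventilation characteristics". With ventilation parameters among the secondary outcomes, leaving them out of the main models is coherent. This stands. A reader might infer that the plan promises independence from ventilation and then fails to deliver it; the documents do not support that. What remains is that the term is undefined and that a reader could take it to cover ventilation.

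**The link to the outcome is thin.** The Rationale speaks of lung-protective ventilation as a strategy and ties hypocapnia to VT or RR only as a possibility. Study design says that both trials used low tidal volumes, which probably narrows VT variation, and no section states an effect of RR on PPCs. This stands too, and it limits the likely size.

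**Adjustment is imperfect.** Hypocapnia counts from a single low reading anywhere between study start and end (Patient categories), so early VT and RR may follow a low etCO2 or have been changed because of it. In assumed scenarios of that kind, adjustment moved a spurious OR of 1.13 to 1.12 or 1.19, and one of 1.23 to 1.16 or left it at 1.23. With another unmeasured cause of low etCO2, and no effect of ventilation on PPCs, adjustment raised the OR slightly, for example from 1.23 to 1.26. The added model therefore cannot settle the matter. It would show how sensitive the estimate is, which no planned analysis does.

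**Conclusion.** The gap is real and modest. The documents establish that the plan raises VT and RR as possible sources of hypocapnia, connects ventilation strategy with PPCs, holds the data, and adjusts for neither variable anywhere. The planned estimates therefore cannot say whether a hypocapnia–PPC association is separate from VT and RR.

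The documents do not establish the size or direction of any bias. The figures of 1.00 to 1.23, and up to 1.64 under stronger assumptions, show only what could occur; no correlation or effect behind them comes from the plan. A reader might conclude that the planned estimates are biased, or that hypocapnia merely marks aggressive ventilation. Neither follows, and the bias may be small or nil. The planned covariate set is not wrong for an association adjusted for those six variables. The change is worth making because it is cheap and determines what 'independent' can be taken to mean. Confidence is medium.

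**What to change.** Keep the propensity match and the mixed model as planned, and make three additions.

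1. **Statistical analysis plan.** Add one sensitivity analysis: the generalized mixed model with the same etCO2 term and covariates, plus VT (ml/kg predicted body weight) and RR from the first recorded time point. Fit the versions with and without VT and RR to the same patients. Report both estimates side by side with confidence intervals, and describe the change without a pass/fail rule.
2. **Report wording.** Define 'independent' as 'after adjustment for the listed covariates', and claim no independence from ventilation settings on the planned models alone.
3. **Stated limits.** VT and RR are also secondary outcomes; early values may follow or respond to a low etCO2; and one early value removes only part of any confounding.

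A second propensity match that adds VT and RR is not advised. If etCO2 tracks ventilation closely it can lose many pairs: under assumed inputs about 65% of the smaller group was kept at a correlation of -0.65, and 47% at -0.8. A shift in the estimate would then mix selection with confounding.

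Cost: a few lines of SAP text and one extra model on data already held. The added model will have a wider confidence interval, with a standard error about 1–9% larger under moderate assumed correlations and up to about 1.3 times if etCO2 follows VT and RR closely.

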#### Hypothesis

Intraoperative hypocapnia has an independent association with patient demographics, ventilation parameters, and perioperative complications.

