### Study design

For this analysis we will use the database of the two randomized clinical trials, named the 'High versus Low Positive End–expiratory Pressure During General Anesthesia for Open Abdominal Surgery (PROVHILO) [3], and the 'PRotective Ventilation with Higher versus Lower PEEP during General Anesthesia for Surgery in OBESE Patients' (PROBESE) [9]. PROVHILO and PROBESE investigated the effects of an open lung approach during low tidal volume ventilation in patients undergoing major surgery.

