#### **Patient categories**

We will use the intraoperatively collected  $etCO_2$  levels to classify patients as either 'with hypocapnia' or 'without hypercapnia', using the cutoff of 35 mmHg. A patient is considered 'hypocapnic' if the  $etCO_2$  was < 35 mm Hg at any point during surgery, from start of the study till end of the study, and classified as 'without hypocapnia' otherwise. In case of a missing value immediately before extubation, we will use the values as reported in the last hour of surgery [10].

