# Calculations

Intraoperative ventilation variables collected in the parent studies included tidal volume  $(V_T)$ , positive end–expiratory pressure (PEEP), plateau or maximum airway pressure (Pplat or Pmax) and respiratory rate (RR).

Ventilation parameters are calculated as follows:

For  $V_T$ , expressed in ml/kg predicted body weight:

50 kg + 2.3 kg (height in inches -60) (in males)

45.5 kg + 2.3 Kg (height in inches -60) (in females)

For driving pressure ( $\Delta P$ ):

 $\Delta P = Pplat - PEEP$  (with volume–controlled ventilation [VCV])

 $\Delta P = Pmax - PEEP$  (with pressure-controlled ventilation [PCV]) [11] For mechanical power of ventilation (MP):

MP = 0.098 \* VT \* RR\* (Ppeak – 0.5 \* ΔP) (with VCV) [12]

MP = 0.098 \* VT \* RR \* (Pmax – 0.5 \* ΔP) (with PCV) [13]

For respiratory system compliance (CRS):

$$C_{RS} = V_T / \Delta P$$

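### The hypothesis claims an independent association of hypocapnia with demographics that no planned analysis can support, and the plan names no analysis for ventilation parameters

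*Combined protocol and SAP*

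**What the plan says.** The Hypothesis section names three domains and applies the word *independent* to all of them: "Intraoperative hypocapnia has an independent association with patient demographics, ventilation parameters, and perioperative complications". The Objectives section is weaker: "The current analysis will assess associations of intraoperative hypocapnia with patient demographics, ventilation characteristics", followed by complications and length of stay, without that word. The Rationale also speaks only of associations. It notes that hypocapnia is common, "possibly meaning that anesthesiologists continue to use high, if not too high respiratory rates or tidal volumes".

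The data come from two trials, PROVHILO and PROBESE. The title of the latter is given as "PRotective Ventilation with Higher versus Lower PEEP during General Anesthesia for Surgery in OBESE Patients". A patient is hypocapnic if etCO2 falls below 35 mmHg "at any point during surgery, from start of the study till end of the study".

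The Statistical analysis plan section treats the domains differently:

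- **Demographics.** "Differences in baseline characteristics between patients with and patients without hypocapnia will be analyzed using the Pearson" chi-squared or Fisher test if categorical, and by ANOVA or Kruskal-Wallis if continuous.
- **Ventilation parameters.** Four time points are given (hours one to three, and before extubation). No test or model is named. The Calculations section confirms that the data exist ("Intraoperative ventilation variables collected in the parent studies included tidal volume", and respiratory rate among others). The Study outcomes section classes these parameters as outcomes: "Secondary outcomes include intraoperative complications, a set of intraoperative ventilation parameters, intraoperative vital signs".
- **Complications.** The primary outcome, postoperative pulmonary complications, gets a generalized mixed model with six covariates. A 1:1 propensity-matched cohort on the same six is also planned, but the outcomes to be compared in it are not listed.

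**The concern.** An independent association is one that remains after other relevant variables are accounted for. A one-variable test cannot establish that, so if the plan is followed as written, a report that age, sex or BMI is independently associated with hypocapnia would have nothing behind it.

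Pooling makes this sharper. One trial enrolled obese patients, so BMI and trial are tied together. If anesthetic practice, centres or type of surgery led to different hypocapnia rates in the two trials, a pooled BMI test would pick up that difference as if it were a BMI effect.

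For ventilation parameters the problem is one of specification. The Rationale suggests respiratory rate and tidal volume as a possible explanation of hypocapnia, yet the plan does not say how either will be compared between groups, crudely or with adjustment. The choice would be made after the data are seen.

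**Working it through.** The plan gives no figure to reproduce: the sample size is whatever is available, and no hypocapnia rate or BMI distribution is stated. The check is to take each planned analysis and ask what it explains and what it adjusts for.

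| Planned analysis | What is explained or compared | Adjusted for | Can it show independence for demographics? | For ventilation parameters? |
|---|---|---|---|---|
| Two-group baseline tests | Each characteristic by hypocapnia | Nothing | No | Not mentioned |
| Propensity-matched cohort | Outcomes by hypocapnia; outcomes not listed | Age, sex, BMI, surgery type, COPD history, compliance | No: balanced by design | Possibly, except compliance; not stated |
| Generalized mixed model | Primary outcome by etCO2 | The same six | No: coefficients describe complications | No |
| Obese / non-obese repeat | Main analyses within BMI groups | Stratifies by BMI only | No | Not stated |
| PEEP interaction | Primary outcome | As mixed model | No | No |
| By-trial characteristics table (Planned inserts, eTable 1) | Descriptive | Nothing | No | No |

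Estimating a propensity score does require a model of hypocapnia on the six covariates. The plan uses it only to match, does not propose to report its coefficients, and lists no trial term.

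**Illustration of the pooling problem. All inputs are assumed; this is not a measure of size.** Let G be the gap in mean BMI between trials (8 to 12 kg/m²), r the PROBESE:PROVHILO size ratio (1 to 2), and hA and hB the hypocapnia rates in PROBESE and PROVHILO. Assume no BMI–hypocapnia association within either trial. The pooled difference in mean BMI, hypocapnic minus non-hypocapnic, is G × (sH − sN), where

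- sH = r·hA / (r·hA + hB)
- sN = r(1 − hA) / [r(1 − hA) + (1 − hB)]

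Examples:

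- 70% vs 60%, r = 1, G = 12: sH = 0.70/1.30 = 0.538, sN = 0.30/0.70 = 0.429; difference 12 × 0.110 = 1.32. With r = 2 and G = 8: 8 × (0.70 − 0.60) = 0.80.
- 65% vs 60%, r = 1, G = 12: 12 × (0.520 − 0.467) = 0.64. With r = 2 and G = 8: 8 × (0.684 − 0.636) = 0.38.
- 60% vs 70%: the sign reverses, from −1.32 to −0.77.
- Equal rates: 0.

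A spurious BMI difference can therefore arise in either direction, and it vanishes as the two trials' rates converge.

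**Price of adding trial to a model with continuous BMI.** In a linear approximation the variance inflation is 1 + p(1 − p)G²/S², with p = r/(1 + r) and an assumed within-trial SD S of 4 to 6.

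- Smallest: 1 + 0.222 × 64/36 = 1.40, standard error × 1.18.
- Largest: 1 + 0.25 × 144/16 = 3.25, standard error × 1.80.

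**The case against.** The strongest reply has four parts.

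*The matched cohort covers ventilation parameters.* They are listed as secondary outcomes, and the plan does not restrict which outcomes are compared after matching. This stands in part. A reader might infer from the table that the plan has no adjusted analysis for ventilation parameters at all. The documents do not support that: tidal volume, respiratory rate, PEEP and driving pressure could be compared in the matched cohort. What can be said is that the plan names no test for them and leaves the cohort's scope open. Only compliance is ruled out.

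*For demographics it is one word.* The Objectives and Rationale ask only for associations, and two-group tests deliver those. That is fair, and it is why a wording change is an acceptable fallback. But the hypothesis is the statement being tested, and it says more than the objective does.

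*The obesity split deals with BMI.* If every PROBESE patient is obese, the non-obese group contains PROVHILO patients only, and trial mixing cannot occur there. This is correct as far as it goes. Mixing can persist in the obese group, and the plan does not say that the baseline tests are among the analyses repeated.

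*The BMI figures depend on chosen inputs.* They do. A reader might take a difference of about 1 kg/m² as the expected error. Nothing in the documents supports that: a 5-point gap in rates gives only about 0.4 to 0.6, and equal rates give zero.

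**Conclusion.** The mismatch is real and limited. For demographics, no planned and reported analysis can support an independent association with hypocapnia. For ventilation parameters other than compliance, the analysis is unspecified, not absent. In size, that is one of three domains with crude tests only and a second with no named test.

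This conclusion rests on the text alone and on the ordinary meaning of *independent* as adjusted. It does not depend on the BMI illustration, which shows only the mechanism. The adjusted analysis of the primary outcome is not affected, and nobody should infer that it is. The change is worth making because the data are already held and these associations are part of the study's stated purpose.

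**What to change.** 1. Add one multivariable logistic model with hypocapnia, as defined under Patient categories, as the dependent variable. Enter the demographic variables together, with trial as a fixed stratum and centre as a random intercept if centre identifiers are available. Keep BMI continuous and show its coefficient with and without the trial term, because adjusting for trial also removes any between-trial difference that is truly due to BMI.
2. State that ventilation parameters other than compliance will be compared between groups in the matched cohort, and name the test. Report these as associations only: hypocapnia is counted at any time during surgery, so a recorded setting may come before or after the low reading. A further model with ventilator settings as predictors of hypocapnia is optional and open to debate, since the plan classes them as outcomes.
3. If the model in item 1 is not added, limit *independent* in the Hypothesis section to the adjusted outcome analyses, use the Objectives' wording elsewhere, and label the one-variable tests descriptive.

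The cost of items 1 and 2 is modest extra analysis on existing data and a wider interval for BMI once trial is included (standard error roughly 1.2 to 1.8 times larger under the assumed inputs above). Item 3 costs only an edit.
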